The primary aim of the proposed study is to evaluate the change in global CBF with ACZ, so the primary outcome is the change in global CBF after 24 weeks relative to pre-treatment baseline. Based on the preliminary data, we expect to see a 15% difference between the ACZ treatment and placebo groups on the improvement in global cerebral perfusion with standard deviation (SD) of 30%. We ran Monte Carlo simulations under a linear mixed effect model (same model as planned for analysis) and calculated a needed total sample size of n=50 to detect a group difference of 0.5 SD at the 24 weeks (phase 1) assuming a within-subject correlation of 0.5, a significance level of 0.05, and 90% power. We hypothesize a similar group difference in phase 2 (ACZ-ACZ group would not change between weeks 24 and 48 but delayed-start group would improve) and similar power to detect this effect. With 50 patients, for Aim 1.2, we will have 80% power to detect an average correlation as low as 0.39 between CBF and MD or FA. Considering a dropout rate of 18%, we need to recruit 60 participants. Aims 2 are mainly exploratory and parameters derived from this study will be used to help design future larger scale confirmatory studies.

All analyses will be intent-to-treat. To summarize the data, descriptive statistics will be used. Demographics and baseline characteristics at randomization will be summarized for each treatment arm. Generalized linear mixed models will be used to analyze all outcomes and will include treatment group and time, group-by-time interaction, and disease duration (stratifying variable) as covariates, and a random intercept to account for within-patient correlation.

For the primary outcome, we will focus on comparing the treatment groups in phase 1. A linear mixed model will be used to compare the estimated change in global CBF between baseline and week 24 in the ACZ and delayed-start groups. A secondary analysis will study ACZ treatment effect on CBF in different regions by treating regions as clusters in the linear mixed model. If normality of CBF outcome does not hold, an appropriate transformation or different outcome distribution will be used.

For the secondary endpoint at 48 weeks (phase 2), a similar mixed model will be used to compare changes in global CBF between weeks 24 and 48 weeks in the early-start and delayed-start groups. The model will include the same terms as for phase 1.

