Secondary outcomes considers repeated measures of MD or FA at different time in different regions. Linear mixed models will be used to evaluate changes in MD and FA from baseline (24 weeks for delayed-start) to 24 weeks (48 weeks for delayed-start) after ACZ therapy. These changes will be compared between regions with and without increased CBF (>15% difference from baseline). Terms in the model will be as for CBF with the addition of increased CBF (yes/no) for the region. Mixed models will also be used to compare MD and FA changes between white matter areas with and without lesions.

Logistic or linear mixed models will be used to evaluate change from baseline to after 24 week ACZ therapy (using phase 1 and phase 2 data) in the tertiary composite change outcome. Models will include the same terms as for analyses of the primary outcome. We will evaluate associations between changes in clinical outcomes and changes in CBF, CBV, and MTT by including each of these variables (one at a time) as a time-varying covariate.

As this trial uses a small sample size, we would not expect statistically significant treatment effects on clinical disability though this exploratory measure should be useful in power calculation for the anticipated larger, randomized clinical trial.

ETHICAL CONSIDERATIONS

Informed Consent

The informed consent form is a method of providing information regarding the trial to a prospective participant and allows for an informed decision about participation in the study. All participants (or their legally acceptable representative) must read, sign, and date a consent form before participating in the study, taking study drug, and/or undergoing any study-specific procedures. If a participant does not speak and read English, the consent materials will be translated into the Spanish.

The informed consent form will be updated or revised whenever important new safety information is available, whenever the protocol is amended, and/or whenever any new information becomes available that may affect a subject's participation in the trial.

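### The MD/FA model names no CBF-status-by-time term, so its added yes/no term estimates a difference in level, not the planned difference in change

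*Combined protocol and SAP*

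**What the plan says.** All of this is in Section 11, Sample Size and Statistical Methods.

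- **Response.** "Secondary outcomes considers repeated measures of MD or FA at different time in different regions". These are levels at each visit and region; a change score is not named.
- **Window.** The models evaluate "changes in MD and FA from baseline (24 weeks for delayed-start) to 24 weeks (48 weeks for delayed-start) after ACZ therapy", that is, weeks 0 to 24 for early start and weeks 24 to 48 for delayed start.
- **Comparison.** "These changes will be compared between regions with and without increased CBF", where increased means more than 15% above baseline.
- **Terms.** "Terms in the model will be as for CBF with the addition of increased CBF (yes/no) for the region".
- **Terms carried over.** The general model "will include treatment group and time, group-by-time interaction, and disease duration (stratifying variable) as covariates, and a random intercept". Its only interaction is group-by-time. For regional CBF, the section adds that regions are treated as clusters.
- **Power for this aim.** With 50 patients, "we will have 80% power to detect an average correlation as low as 0.39 between CBF and MD or FA".

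Under Primary & Key Secondary Objective, better tissue integrity in a proportion of lesions is the key secondary endpoint. The same section also plans to correlate DTI change with CBF increase.

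**The concern.** The comparison sentence and the term list do not match. A difference in change by CBF status needs a term that lets the MD/FA time course differ by CBF status, and none is listed. Group-by-time does not serve, because it contrasts early start with delayed start. Taken literally, the list makes regions with and without increased CBF move in parallel, and the only coefficient involving CBF status is a vertical offset averaged over all visits, the pre-ACZ scan included.

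If the two kinds of region already differ in MD or FA before ACZ, that offset carries the earlier difference. It could then be reported as evidence that better perfusion improved tissue when the changes were equal, or it could cancel a real difference in change. The model bears on the second half of the trial hypothesis, and the protocol intends the results to inform a phase 3 trial.

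**Working it through.** **1. The plan's own figure for this aim.** By Fisher's z at two-sided alpha 0.05 (sidedness is not stated), power = Φ(atanh(0.39) × √(50 − 3) − 1.960) = Φ(0.412 × 6.856 − 1.960) = Φ(0.863) = 0.806. The smallest correlation giving 80% power is tanh((1.960 + 0.842)/6.856) = 0.387. The stated 0.39 reproduces. It is a correlation calculation and does not depend on the model below.

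**2. What the listed terms estimate.** Let T run from 0 (pre-ACZ scan) to 1 (24 weeks on ACZ). Let regions with increased CBF differ from the others by *gap* at T = 0 and by *gap* + *delta* at T = 1, changing linearly. *Delta* is the comparison that the plan states. Fitting CBF status without its interaction with time gives

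coefficient = gap + delta × mean(T).

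The Stage 3 schedule has scans at weeks 0, 6, 12, 18 and 24, so mean(T) = (0 + 0.25 + 0.5 + 0.75 + 1)/5 = 0.5. Two scans only, (0 + 1)/2, also give 0.5. Hence coefficient = gap + delta/2. It is exactly zero when gap = −delta/2.

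**3. Simulation check.** Assumptions not in the documents: 50 patients, 10 regions each, 40% of regions with increased CBF, patient and residual SD 0.7 each, 60 runs per setting. The two variances are 0.49 each, so the correlation is 0.49/0.98 = 0.5. This matches the primary calculation, made "assuming a within-subject correlation of 0.5, a significance level of 0.05, and 90% power". The total SD is about 0.99, so effects are roughly in SD units. Each cell gives the mean estimate and the share of runs with p < 0.05.

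| Gap | Delta | Visits | gap + delta/2 | Listed terms: CBF status | With CBF status by time, last visit |
|---|---|---|---|---|---|
| 0.5 | 0 | 2 | 0.50 | 0.497 (100%) | −0.016 (3%) |
| 0.5 | 0 | 5 | 0.50 | 0.498 (100%) | −0.012 (5%) |
| 0 | 0.5 | 2 | 0.25 | 0.257 (100%) | 0.498 (100%) |
| 0 | 0.5 | 5 | 0.25 | 0.257 (100%) | 0.516 (100%) |
| −0.25 | 0.5 | 2 | 0 | −0.010 (3%) | 0.504 (100%) |
| −0.25 | 0.5 | 5 | 0 | −0.002 (7%) | 0.478 (100%) |

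The listed terms follow the formula. The interaction recovers delta in every row.

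**4. Does region clustering matter?** A second set of runs used an FA-like scale, again assumed: 50 patients, 8 regions, 5 visits, SD 0.02 each for patient, region and residual.

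- Gap 0.01, delta 0: CBF status averages 0.010 and is significant in 99 to 100% of runs, with or without a region effect in the model. Clustering does not cure the problem.
- Gap −0.01, delta 0.02: CBF status averages about 0, as −0.01 + 0.02/2 = 0. It is significant in 21 to 24% of runs without a region effect and in 2 to 3% with one. That excess comes from ignoring regions, not from the missing interaction.
- Interaction when delta is 0: it is significant in 0 to 1% of runs without a region effect and in 3 to 7% with one, against a nominal 5%.

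The interaction corrects what is estimated. The region clusters correct its standard error.

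**The case against.** **The term list may be shorthand.** Section 11 never says main effect only, and it states the target correctly. That is fair. But the same section writes out group-by-time where it wants an interaction, and here adds only the yes/no term. Followed as written, the list answers a different question.

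**The response may be a change score.** The primary outcome is a change in CBF, and repeated changes at weeks 6 to 24 could keep the time terms. On this reading the yes/no term is the right contrast: in simulated week-24 change scores it averaged 0.000 when the truth was 0 and about 0.020 when the truth was 0.02, at every baseline gap tried. The reading is possible, but it fits poorly with a response described as repeated measures of MD or FA. The plan should say so if it is meant.

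**The yes/no term may vary over time, being 0 before ACZ.** With a patient intercept only, its coefficient was still 0.465 to 0.484 when gap was 0.5 and delta 0. When gap was −0.25 and delta 0.5, it was 0.254 with two visits and 0.064 with five. Adding region clusters reduces the bias without removing it (0.0047 for a gap of 0.010 and delta 0).

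**Stronger readings that a reader might infer.**

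- *The test would mostly reflect anatomy.* The documents do not show this. CBF status depends on each patient's response, and a gap arises only if response is associated with pre-ACZ MD or FA. The Background describes regional perfusion differences and more lesions in regions expected to be hypoperfused. That makes an association plausible, but no MD or FA values are given.
- *This is the plan's only link between perfusion and tissue integrity.* It is not. The objectives section also plans a DTI–CBF correlation, a rank correlation of the T1/T2 lesion ratio with CBF, CBV and MTT, and a relaxometry comparison by CBF change.
- *The main result is at risk.* The primary comparison of global CBF does not use this term.

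**Conclusion.** The point holds for the model as listed. With repeated MD/FA levels as the response and CBF status fixed per region, no coefficient carries the comparison that Section 11 announces. The yes/no coefficient is the baseline gap plus half the difference in change, given linear change and even visits. With no gap it reports half the true difference. With a gap and no difference in change it can be significant in essentially every run. With a gap of minus half the true difference it averages zero.

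The formula does not depend on the assumed SDs or on the numbers of patients and regions. The rejection rates do, and the gap itself is an assumption, so the actual size in this trial cannot be stated. The reach is limited to a secondary analysis in a pilot, though one that serves the key tissue-integrity endpoint. The primary analysis and the power statement for a correlation of 0.39 stand. Severity: should-fix.

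**What to change.** In the secondary-outcomes paragraph of Section 11, choose one of two statements before the data are analysed.

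1. Keep MD and FA levels as the response. Add the interaction of increased CBF (yes/no) with time since the pre-ACZ scan (week 0 for early start, week 24 for delayed start). Name that interaction at the end of the 24-week on-ACZ window as the tested quantity for MD and for FA. State that regions are nested in patients as clusters, in line with the regional CBF analysis. A fixed region factor is a possible alternative but is not required.
2. Or state that the response is the within-region change in MD or FA from the pre-ACZ scan. The yes/no term is then the right contrast, and the list of terms can otherwise stay.

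The cost is one sentence. The scans, patients and sample size do not change.

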This study will include analysis to determine if therapy with oral divided-dose ACZ impacts global measures of clinical disability. Change in clinical disability measures assessed using the multiple sclerosis functional composite scale (MSFC) and the expanded disability status scale (EDSS) will be correlated with CBF, CBV and MTT. In addition, patient reported clinical outcome measures will be assessed at each time point. As this trial uses a small sample size, we would not expect statistically significant treatment effects on clinical disability though this exploratory measure should be useful in power calculation for the anticipated larger, randomized clinical trial.

Potential Risks and Benefits:

End Points - Efficacy

Altered cerebral perfusion has been previously reported in patients with MS. Global, regional and lesional changes in perfusion have been documented and some have found associations between decreased regional CBF and T2 lesion volume (Ota et al., 2013).

There are several currently approved treatments for MS that, in the aggregate, decrease the potential for formation of new MRI lesions. However, none have been clearly shown to impact the evolution of lesions, once formed. Several studies have shown that clinical disability correlates better with tissue integrity within black holes (Parry et al., 2002; Truyen et al., 1996; van Walderveen et al., 1999b). ACZ is a generally well tolerated therapy that has previously been shown to transiently increase cerebral perfusion. Long-term use of ACZ might more persistently improve global or regional CBF and could increase the proportion of lesions with improved tissue integrity.

End Points - Safety

ACZ is generally well tolerated with few reported adverse events (AEs). Transient perioral numbness has been reported in patients receiving bolus of IV ACZ. Hypersensitivity reactions, including diffuse pruritus, hives and shortness of breath have been reported with repeat administration of either IV or oral medication. A complete list of AEs is available in the package insert (see section 7) and will be provided to subjects with the informed consent.

Subjects will have face-to-face clinical evaluations at each scheduled visit (see section 4), will have monthly telephone or email contacts during the course of study and encouraged to report any AE occurring with drug at any point during the study. Any subject who is unable to tolerate study medication will be withdrawn from the study.

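### The clinical-perfusion analysis aims at associations between changes, but one time-varying covariate in a random-intercept model does not isolate them if levels are entered, and the plan does not say whether levels or changes are meant

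*Combined protocol and SAP*

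**What the plan says.** The tertiary paragraph of Sample Size and Statistical Methods states the target: "We will evaluate associations between changes in clinical outcomes and changes in CBF, CBV, and MTT". The method is to relate clinical change to "changes in CBF, CBV, and MTT by including each of these variables (one at a time) as a time-varying covariate".

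The host model is described in two places. The general paragraph of that section says the mixed models "will include treatment group and time, group-by-time interaction, and disease duration (stratifying variable) as covariates", together with "a random intercept to account for within-patient correlation". The tertiary paragraph adds: "Models will include the same terms as for analyses of the primary outcome". No term for the patient's mean perfusion or for baseline perfusion is named.

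The form of the two sides is left open:

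- **Outcome.** The tertiary models are to "evaluate change from baseline to after 24 week ACZ therapy (using phase 1 and phase 2 data) in the tertiary composite change outcome". This could mean a change score, or a contrast estimated from repeated levels.
- **Covariate.** In the methods sentence, the variables referred to could be CBF, CBV and MTT themselves or their changes. Tertiary Objectives says that change in MSFC and the "expanded disability status scale (EDSS) will be correlated with CBF, CBV and MTT", with no mention of change on the perfusion side.

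**The concern.** An association between changes is a within-patient quantity: when this patient's perfusion rises, does this patient's disability score move? A level that varies over visits carries two kinds of information, namely how the patient differs from other patients and how this visit differs from the patient's other visits. A random-intercept model with one coefficient pools the two. If patients with lower perfusion are also more disabled, that cross-sectional difference enters the coefficient even when nothing moves together within patients.

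The protocol's background makes such a difference plausible. End Points - Efficacy notes that "some have found associations between decreased regional CBF and T2 lesion volume", and the introduction links lesion measures to disability.

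The mixing is heaviest with few visits. That matters most for CBV and MTT, which come only from the contrast scans every 12 weeks. The clinical results are meant to help power a later trial, so a coefficient for the wrong quantity could misinform that planning.

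**Working it through.** **Plan's own figure.** No figure is given for this analysis. The nearest is a detectable correlation of 0.39 between CBF and MD or FA (80% power, 50 patients). By Fisher's z, n = ((1.960 + 0.842)/atanh 0.39)² + 3 = 49.3, so 50, with 80.6% power at 50. The figure reproduces, but it says nothing about clinical outcomes.

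**Inputs.**

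- 50 analysed patients; alpha 0.05, taken as two-sided (Sample Size and Statistical Methods).
- Visits (Stage 3 table in Trial Schedule): pCASL CBF at 5 visits to week 24 and 9 to week 48; contrast-based CBV and MTT at 3 and 5.
- Covariate within-patient correlation (ICC): 0.5, borrowed from the plan's CBF sample-size assumption.
- Outcome ICC: 0.5, 0.8 or 0.9. Assumed.
- Between-patient correlation r of perfusion and disability levels: 0, 0.3 or 0.5 in size. Assumed.
- True within-patient association: zero.

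**Why the coefficient is a mix.** With T visits and unit total variances, the random-intercept estimate is approximately

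β = (W·β_within + ψ·B·β_between)/(W + ψ·B),

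where, per patient,

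- W = (T−1)(1−ICC_x)
- B = T·(ICC_x + (1−ICC_x)/T)
- ψ = (1−ICC_y)/((1−ICC_y) + T·ICC_y)
- β_between = r·√(ICC_x·ICC_y)/(ICC_x + (1−ICC_x)/T)

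Example with T = 5, both ICCs 0.5, r = 0.5: W = 2.0, B = 3.0, ψ = 0.5/3.0 = 0.167. The weight on the between-patient slope is 0.5/2.5 = 0.20. β_between = 0.25/0.6 = 0.417. So β ≈ 0.20 × 0.417 = 0.083, although the within-patient slope is zero. Simulation gives 0.092.

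With T = 9: W = 4.0, B = 5.0, ψ = 0.1. The weight is 0.5/4.5 = 0.111, β_between = 0.25/0.556 = 0.45, and β ≈ 0.050. Simulation gives 0.051.

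With T = 3: W = 1.0, B = 2.0, ψ = 0.25. The weight is 0.5/1.5 = 0.33, the largest of the three.

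**False-positive rates.** These come from simulations of a REML random-intercept model with group-by-visit terms, 1,500 trials per cell, Monte Carlo error about 0.6 points at 5%. Levels are entered on both sides. Each cell shows r = 0.3 / r = 0.5.

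| Visits | Outcome ICC 0.5 | 0.8 | 0.9 |
|---|---|---|---|
| 3 | 17% / 38% | 11% / 22% | 8% / 15% |
| 5 | 14.1% / 30.5% | 7.7% / 13.3% | 6.7% / 8.9% |
| 9 | 9.5% / 20.1% | 6.9% / 9.0% | 6.0% / 7.3% |

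Repeat runs move single cells by a point or two. Across runs the ranges are 6-38% (3 visits), 7-32% (5) and 4-20% (9); the low ends are close to nominal.

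**Sensitivity.**

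- r = 0: 4.8-6.5%, no inflation.
- Change from baseline on both sides: 4.1-5.8%. On one side only: 4.1-6.6%.
- Covariate ICC 0.8, 5 visits: 25.2% / 62.5%, 14.7% / 34.9% and 10.5% / 20.3% for outcome ICC 0.5, 0.8 and 0.9.
- Patient mean plus deviation, testing the deviation: 4.3-6.3% throughout.
- Baseline value in place of the patient mean (r = 0.5, outcome ICC 0.5): about 9-10% with the baseline row kept, and 17.8%, 12.6% and 10.0% at 3, 5 and 10 visits on post-baseline rows only.

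**The error can also hide an effect.** Take a within-patient correlation of about 0.25 opposite in sign to a between-patient correlation of 0.5 in size, with 3 visits and outcome ICC 0.5. The single coefficient is significant in 15% of runs and the deviation coefficient in 70%.

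**The case against.** A reader might infer that the plan does enter raw levels and will therefore declare false associations too often. The documents do not support that as a fact.

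- **The text never says levels.** The sentence names changes on both sides just before describing the covariate, the outcome is called a change outcome, and the preceding paragraph defines increased CBF by its difference from baseline. If changes are entered on both sides, the inflation disappears. This stands as a limit on the point. Levels remain likelier because the objectives correlate clinical change with CBF, CBV and MTT as such, and because the model terms are carried over from the primary analysis, where change is estimated from repeated measurements.
- **The between-patient correlation is not documented.** The background statement concerns regional CBF and T2 lesion volume. It does not mention EDSS, MSFC, CBV, MTT or global CBF. At zero correlation there is no inflation. This stands too, so every rate above zero correlation is conditional.
- **The upper rates need an unstable outcome.** Patients must have had unchanged therapy for six months, so disability scores may be steadier than an ICC of 0.5. At 0.8 to 0.9 the rates are much lower. A steadier covariate would raise them again, and the documents give neither ICC.

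A reader might also infer that the later trial would be built on this coefficient. The plan says only that the exploratory clinical measure should help in its power calculation.

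**Conclusion.** The point holds conditionally. The plan names a within-patient target but does not specify the form of the covariate. Under the likelier reading, the fitted coefficient mixes within- and between-patient slopes and so does not estimate that target. Whether this also yields excess false positives depends on a between-patient correlation that the documents do not give. With an assumed size of 0.3 to 0.5 and a covariate ICC of 0.5, the rates run from near nominal to 38%, worst for CBV and MTT in a single 24-week window and smallest with many visits and a stable outcome. Only the linear model was simulated, not the logistic option.

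The analysis is exploratory, and no primary or key secondary conclusion is touched. The gain is an estimate of the right quantity for planning the later trial, and that is worth a sentence in the plan.

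**What to change.** State whether levels or changes are entered for the outcome and for each perfusion variable. If levels, split each of CBF, CBV and MTT into the patient's own mean over the visits analysed and the visit's deviation from that mean. Enter both, and report the deviation coefficient as the association between changes. The coefficient of the mean can be shown separately as the cross-sectional association.

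Do not use the baseline value in place of the patient mean. A single baseline reading is a noisy stand-in for the patient's usual level, so between-patient differences still leak into the other term.

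The cost is a sentence or two in the analysis plan and no new data. There is some loss of precision if the within- and between-patient slopes are in fact equal, because the between-patient information is then no longer used.
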